## iv. Additional Analysis

A sub-analysis will be done on the intervention group to determine if levels of engagement with the educational materials have impact on the primary and secondary outcomes. Level of engagement will be determined by participants self-report of reading/viewing.

Additionally, we will look at the interaction between the intervention group and other population risk factors to see if there are other effect modifications.

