### **Enrollment Criteria for Aim 3**

Parent Recruitment & screening: Parents who have consented to be in the study at Aim 2 and completed baseline surveys will be invited to participate in the study. These parents will have an index child who attended K-5 schools that were randomized to receive the ROSSEY intervention. There are approximately 290 parents in our database who meet these inclusion criteria. The research team will work with CCHP staff to contact parents, solicit their interest, answer questions, and consent them into the study. CCHP staff will then coordinate scheduling four (4) focus group discussions; two of them will be in English and the other two will be in Spanish.

Enrollment: Interested parents will participate by completing one focus group.

Student Recruitment & screening: Parents who have participated in Aim 3 focus groups will be asked by research staff whether their children can be contacted to participate in semi-structured interviews. Parents who give their permission will be identified and a list generated for contacting students. Research staff will contact students via phone or in-person. and provide study information and answer questions. Expectations for participating in the study will be shared with potential participants

School staff and administrators Recruitment & screening: Research staff will work with YSD contact to identify school staff and administrators appropriate for participating in Aim 3 1:1 semi-structured interview. We will aim to recruit one (1) superintendent who oversaw the school district's implementation of COVID-19 mitigation strategies, seven (7) principals who worked at the schools that were randomized to the ROSSEY intervention, six (6) teachers who work at schools randomized to the ROSSEY intervention, and six (6) school nurses. We will also plan to interview [name], as she helped oversee the implementation and management of the COVID-19 mitigation strategies at the schools.

Enrollment: Interested school staff and administrators will participate by completing a 1:1 semi-structured interview and complete a one-time online demographic survey delivered through REDCap or by paper.

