## 2. Study Schema and objectives

[figure not shown]
Purpose:	To determine the effectiveness of risk communication for parents and students on students' attendance to school, COVID-19 testing and vaccine uptake
Design:	A clustered randomized controlled trial of risk communication intervention
Central Hypotheses:	Our central hypotheses are that students and parents who view the risk communications will be more likely to have less school absence, increased covid-19 testing and vaccine uptake.
Primary Objectives:	

• To determine if implementing three COVID-19 education comic books for children and two COVID-19 education videos for parents will lower school absenteeism, increase COVID-19 testing, and vaccine uptake in children.

Secondary Objectives:	

• To determine if implementing three COVID-19 education comics books for children and two COVID-19 education videos for parents will increase physical activity, improve sleep, increase emotional regulation in children.

• To determine if implementing three COVID-19 education comics books for children and two COVID-19 education videos for parents will increase physical activity, improve sleep, decrease depression and anxiety in parents

Population:	Children ages 5-13 enrolled in kindergarten to 5 th grade in Yakima School District
Study Size:	14 schools randomized; 7 to intervention and 7 to comparison arms with 450 children in each arm; a total of 900 children from 14 schools.
Primary Outcome Measurements:	

A. Attendance captured through the school district

B. COVID-19 testing data available through the school district testing program and self-reported survey

C. COVID-19 vaccine data available through self-reported survey

Study Duration:	2 years including enrollment period, 2 months to deliver the intervention, 5 months for post 1 survey, 7 months weeks for post 2 survey.

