### Study Timeline

## 4. Sample size and power

**For month 5 outcome.** We will enroll 900 elementary school students from 14 schools in the Yakima School District during the 2022-2023 school year. The sample size of 7 schools per study arm and an average of 50 students per school will provide 90% power to detect a difference of at least 4 hours per week ( $SD=8.0$ ) of in-person school attendance between the intervention and control groups, while assuming intra-cluster correlation (ICC) of 0.05 and type I error rate of 0.05. The estimated sample size of 14 schools with 900 students provides 80% power to detect a difference of 20% or more in COVID-19 vaccination rates between the two study arms, assuming ICC of 0.05 and type I error rate of 0.05.

Minimum detectable difference in hours per week between intervention arms in proposed cluster RCT assuming enrollment of 15 students per classroom, 80% power and two-sided type I error rate of 0.05.					
		Two Arm			
	Number of clusters per arm	30		40	
	ICC	.01	.10	.01	.10
Standard Deviation	5.0	1.0	1.5	.87	1.3
	7.5	1.5	2.2	1.3	1.9

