## 7. Outcome Definitions

### a. Primary Outcomes

The three co-primary outcomes for the trial are school absenteeism, COVID-19 testing, and COVID-19 vaccine uptake. Absenteeism are the student's school attendance data for 2022-2023 school year, COVID-19 data are captured through school testing and self-reported survey, and COVID-19 vaccine uptake data are captured through self-reported survey. All children and parent data after randomization will be included in the intention to treat analysis.

**Absenteeism:** total number of school days missed by each individual student participant, both for the entire school year and month-by-month, as captured and shared with us by school district administrative data systems. Absenteeism will also be measured by school days missed and will be a count variable.

**COVID-19 testing:** Health reports from the school are provided for the 2021-2022 and 2022-2023 school year that list positive covid test results of study participants with the date of testing and the school of attendance. Positive COVID test results will be a binary yes/no variable.

**COVID-19 vaccine uptake:** Parents are asked at enrollment to report their vaccination status and their child's vaccination status. At post survey 1 and post survey 2 the parent is asked to report if they or their child have received any COVID-19 vaccine or booster since enrollment. Vaccination status will be a binary yes/no variable.

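### The engagement sub-analysis is worded as a test of impact, but it compares self-selected families within one arm and can support only an association

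*SAP*

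**What the plan says.** Under Additional Analysis (section 12c.iv), the SAP states: "A sub-analysis will be done on the intervention group". Its purpose is "to determine if levels of engagement with the educational materials have impact on the primary and secondary outcomes". The exposure is defined in one sentence: "Level of engagement will be determined by participants self-report of reading/viewing". No engagement levels, model, covariates or handling of families without an engagement report are given, and nothing limits how the result may be interpreted.

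Three other parts of the documents bear on this.

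- SAP section 8 makes the randomised group the primary exposure and gives avoidance of selection bias as the reason. SAP section 12c puts all efficacy analyses on an intention-to-treat footing.
- SAP section 7a says "COVID-19 vaccine uptake data are captured through self-reported survey", so this outcome has the same kind of source as engagement. Absenteeism comes from district administrative systems, and positive test results come from school health reports.
- The Protocol (Aim 2 Study Procedures, Secondary Outcome Assessments) collects health literacy at enrolment only. It also collects outcome expectations and self-efficacy in surveys offered at enrolment and later, as possible moderators and mediators. Vaccination status is asked at enrolment (SAP section 7a). The sub-analysis uses none of these.

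**The concern.** Three features combine: there is no randomised comparator, the exposure is chosen by families after allocation, and the stated aim is causal. Families who read the comics and watch the videos may already be more inclined to vaccinate, test or keep children in school. If so, more engaged families would have better outcomes even if the materials changed nothing. Controlling the false discovery rate (SAP section 10) does not help, because the problem is bias and not multiplicity.

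For outcomes that the parent reports, there is a second route. A parent who tends to give favourable answers may over-report both engagement and vaccination.

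At stake is the conclusion drawn from this sub-analysis. Followed as written, it would attach a claim of impact, across all primary and secondary outcomes, to a contrast that cannot carry one.

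**Working it through.** **The plan's own figure.** No figure is stated for this sub-analysis. The trial's main power statement was reproduced to confirm that the inputs are read correctly. SAP section 4 says: "The sample size of 7 schools per study arm and an average of 50 students per school will provide 90% power to detect" 4 hours per week with SD 8.0, "assuming intra-cluster correlation (ICC) of 0.05 and type I error rate of 0.05".

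- Design effect = 1 + (50 − 1) × 0.05 = 3.45.
- Effective n per arm = 7 × 50 / 3.45 = 101.4.
- Non-centrality = 4 / (8 × √(2/101.4)) = 3.56.
- Power from the noncentral t with 2 × (7 − 1) = 12 degrees of freedom = 90.4%, which agrees with the stated 90%.

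**Inputs for the check.**

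- Planned intervention-arm size: 450 children, from "14 schools randomized; 7 to intervention and 7 to comparison arms with 450 children in each arm" (SAP section 2).
- Lower size: 290, from the Protocol's count of intervention-arm parents with baseline data (Enrollment Criteria for Aim 3): "There are approximately 290 parents in our database who meet these inclusion criteria".
- Assumed, not in the documents: half of families are favourable to prevention, attitude drives both engagement and vaccination, engagement is split in two for illustration, and the true effect of the materials is zero.

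**Formula.** With half of families favourable:

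- P(favourable | engaged) = e1 / (e1 + e0)
- P(favourable | not engaged) = (1 − e1) / [(1 − e1) + (1 − e0)]
- Uptake in each group = P(favourable) × v1 + [1 − P(favourable)] × v0

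Here e1 and e0 are the engagement rates, and v1 and v0 the uptake rates, in favourable and other families.

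**Stronger links** (engagement 80% v 40%, uptake 60% v 20%):

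- P(favourable | engaged) = 0.8/1.2 = 0.667, so uptake = 0.667 × 0.6 + 0.333 × 0.2 = 46.7%.
- P(favourable | not engaged) = 0.2/0.8 = 0.25, so uptake = 0.25 × 0.6 + 0.75 × 0.2 = 30.0%.
- False difference: 16.7 points.

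**Weaker links** (engagement 70% v 50%, uptake 50% v 30%):

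- P(favourable | engaged) = 0.7/1.2 = 0.583, so uptake = 41.7%.
- P(favourable | not engaged) = 0.3/0.8 = 0.375, so uptake = 37.5%.
- False difference: 4.2 points.

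**Chance of p < 0.05 with zero true effect** (two-proportion normal approximation, 60% engaged, clustering ignored):

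| Links | Difference | n = 450 | n = 290 |
|---|---|---|---|
| Stronger | 16.7 points | about 95% | about 83% |
| Weaker | 4.2 points | about 14% | about 11% |

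**Simulation with clustering** (2,000 null trials, 7 schools per arm, school SD 0.42 on the logit scale). The within-arm contrast was tested with a Mantel-Haenszel test stratified by school, and the randomised contrast with a cluster-level t-test.

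| Engagement | Uptake | Within-arm rejection, n = 450 | n = 290 |
|---|---|---|---|
| 50/50 | 50/20 | 5% | 5% |
| 60/40 | 50/20 | 26% | 18% |
| 70/30 | 50/20 | 74% | 55% |
| 80/20 | 60/20 | 99.9% | 98% |

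On the same null data, the randomised comparison rejected in 4.3% to 6.4% of trials, close to the nominal 5%.

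**Continuous outcomes** (median split on engagement). The false difference in SD units is 2 × r1 × r2 × 0.798, where r1 is the attitude–engagement correlation and r2 the attitude–outcome correlation.

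- r1 = 0.1, r2 = 0.2: 0.03 SD.
- r1 = 0.3, r2 = 0.5: 0.24 SD, or 2.4 points on the PROMIS T-score (SD 10).

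**The case against.** The best defence is that this is a minor analysis, already kept in its place. It is called a sub-analysis, it follows the primary and secondary sections, and SAP sections 8 and 12c tie efficacy to allocation. That stands. A reader might infer that the analysis could be used to rescue a null primary result, but nothing in the documents lets it replace the intention-to-treat result.

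A reader might also infer that the analysis will probably find that engagement works whether or not the intervention does. The documents do not support this. They give no information on how strongly prior attitude predicts engagement, and under the weaker links a significant result is unlikely (about 14% at n = 450). That 16.7 points lies near the 20-point vaccination difference in SAP section 4 reflects the inputs chosen for the stronger case.

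Other limits also stand.

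- The shared-reporter argument does not extend to district attendance records or school test reports.
- The post-surveys ask about any vaccine or booster since enrolment. Families already favourable may have been vaccinated before then, so the assumed contrasts in uptake are not assured.
- The SAP speaks of levels, not a two-way split. The bias is the same in kind, but its size would differ.
- Saying nothing about adjustment is not a plan to leave the contrast unadjusted.

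None of this removes the central point: a within-arm comparison by self-chosen engagement is not randomised, and the SAP describes it as determining impact.

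**Conclusion.** The point holds as one about interpretation of a non-primary analysis. As written, section 12c.iv would support a causal conclusion that its design cannot give. With zero true effect, the false difference in vaccine uptake is 4.2 to 16.7 points under the two illustrative cases. It shrinks as the links weaken and disappears if engagement is unrelated to prior attitude. These sizes rest wholly on the assumed links and on a binary split. They show what can happen and do not predict what will. Correlated self-report, which could affect parent-reported outcomes only, is not included in them. The trial's randomised conclusions do not depend on this analysis, so the priority is low.

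**What to change.** In SAP section 12c.iv:

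1. Change the aim from impact to association, and label the analysis exploratory.
2. Define the engagement levels, and say how families with no engagement report are handled.
3. Adjust for vaccination status, health literacy, outcome expectations and self-efficacy, using enrolment values only. Later values may be affected by the intervention, and adjusting for them would condition on mediators.
4. Keep the school random effect.
5. State that the result does not modify the intention-to-treat conclusion.

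If a causal statement is wanted, a complier-average estimate may be added as an optional exploratory analysis, with randomised arm as the instrument and school clustering, for outcomes measured before the control arm receives the materials. The SAP should then say that it is imprecise, assumes no effect without engagement, relies on the same self-reported engagement, and answers a different question from whether outcomes vary with level of engagement.

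The cost is a few sentences in the SAP, a little more analysis work, and a weaker claim from this sub-analysis. No new data are needed. Adjustment reduces confounding only by the measured traits, so the associational wording is needed even after it.
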